13.1 Sample Size calculations

Recent studies using Alere LAM and sputum Xpert to screen unselected admitted HIV positive patients in Southern Africa^{24,29,31} show that around 17% of these patients are laboratory confirmed for tuberculosis. The added yield of using Xpert Ultra instead of Xpert would involve an 11-17%⁴³⁻⁴⁵ relative increase in bacteriological confirmation. Thus, universal AlereLAM testing and sputum Ultra would likely confirm around 20% of unselected admitted HIV participants in our study. We estimate that the bacteriological confirmation in our control arm would be slightly lower than 20%, around 19%, given that we will not use a universal screening strategy but the WHO recommendations (sputum Ultra if TB compatible symptoms and AlereLAM testing if TB compatible symptoms or in those with advanced HIV disease, or seriously ill, or with a CD4 cell count of less than 200 cells/mm³). Based on existing literature, we estimated that up to 10% of participants in our control arm would not receive either Xpert Ultra or LAM testing.

We estimated that the intervention arm would yield around 26% of bacteriologically confirmed cases by universal testing (irrespective of symptoms) with AlereLAM and Xpert Ultra on sputum, urine, and stool. As mentioned before, universal AlereLAM and sputum Xpert Ultra would yield around 20% of bacteriological confirmation. Studies show that Xpert urine could increase bacteriological confirmation by 4%. Although there is limited evidence on the potential benefits of stool Xpert Ultra in adults, there are promising results observed in children (who, as HIV positive patients, often have extrapulmonary TB). Thus, we assume that adding stool Xpert could increase our bacteriological confirmation about 1%. If we apply a similar gain (observed in sputum) in urine and stool by substituting Xpert by Ultra, the combined added yield would be of around 6%. Thus, we expect to have a 26% bacteriological confirmation in our intervention arm by using universal LAM testing and Xpert Ultra on sputum, stool and urine. This would translate into a 7% difference (19-26%) between our control and intervention arm.

The estimation of the bacteriologically confirmed cases in both the control and intervention arm could have the following limitations:

- We estimate the increased yield of Ultra in urine and stool as if this additionality were independent, considering that this yield would come from potentially different phenotypes of TB patients. Otherwise, some of the gain observed by Urine Xpert Ultra or Stool Xpert Ultra might overlap and thus we could be overestimating the expected additionality in bacteriological confirmation in these samples.
- We obtained the Xpert Ultra added yield from studies performed in TB presumptive HIV positive inpatients and outpatients. Estimates of added yield vary widely in the literature. However, given that major gain of Xpert Ultra has been observed in HIV positive patients and smear negative patients, we think that the added yield of Ultra in our population (strictly admitted PLHIV) could be higher, and potentially greater in extrapulmonary samples such as stool or urine (as a recent study -Kabir et al, 2021 -of Stool Ultra in children

This project is part of the EDCTP2 programme supported by the European Union

has shown). In this regard, we have taken a conservative approach by using the reference of Dorman et al, 2018.

- The added yield of Ultra over Xpert does not consider that some of that additional yield might be picked up by Urine AlereLAM (optimistic approach).
- Some of these limitations may impact both the control and the intervention arm and thus would probably have a limited effect on our expected difference in bacteriologically confirmed cases that we aim to detect through this study.

Assuming that we will find 19% of bacteriologically confirmed cases in the control arm following the WHO indications for sputum Xpert® Ultra and AlereLAM in HIV hospitalized patients (based on previously mentioned data), and a two-sided type I error of 5%, the inclusion of patients per arm would provide an 80% power to detect a 7% increase in the percentage of bacteriologically confirmed TB diagnosis allowing for a loss to follow-up of 5%.

Based on these estimates, the study will require a total of 586 PLHIV participants to be enrolled per trial arm. For both arms together, this yields 1172 patients in total.

Given that 4 sites will be recruiting patients, this means approximately 293 participants per site (around 147 per arm at each site).

13.2 Data analysis

A separate statistical analysis plan will be developed containing all details of the analysis strategy.

13.2.1 Analysis set

We will analyze the data using primarily an intention to treat analysis approach. This dataset is composed for all randomized patients by their assigned intervention. It also includes patients who might not complete week-4 and week-8 visit or who died or who did not receive the full assigned intervention. Lost to follow up patients and deaths will be considered for specific secondary endpoints.

13.2.2 Statistical methods

Variables will be summarized using descriptive statistical methods. Continuous data will be described using the mean and standard deviation statistics when these values follow the normal distribution. Otherwise we will use the median and interquartile range when we will not assume this distribution. Categorical values will be summarized using frequency and/or percentages.

For categorical comparisons we will use a Chi-square test or Fisher exact test according to the

This project is part of the EDCTP2 programme supported by the European Union

data characteristics. Likewise, the continuous comparisons will be tested by Student t-test, Anova test or Kruskal Wallis test.

When necessary, we will transform the continuous data, especially laboratory data, in non-linear scale. For these cases we will describe these data with geometric mean. Heterogeneity between sites will be analyzed.

Assessment of loss to follow-up as random across arms

We will analyze the baseline characteristics between lost and non-lost follow up patients and across arms to ensure that loss to follow up occurs randomly. If we find any significant attribute we will adjust the analysis by this/these factors.

Time-to-event data

Time-to-event data (such as time to mortality, time to TB diagnosis or time to treatment initiation (among lab confirmed or all TB)) will be presented using Kaplan-Meier curves with a log rank test (two-sided 0.05 significance level). The analysis of covariates on time-to-event data will be performed using a Hazard Ratios estimated through Cox regression models.

Comparisons between control and intervention arm will be established at prespecified time points (day 7, day 14, day 28 and day 56). Mean time (and SD) to event per study arm will also be estimated.

Significance levels

The significance level for most comparisons is $p=0.05$. For selected secondary endpoints measured at several timepoints and subgroup analysis, the significance level will be $p=0.01$

Study discontinuations & patient disposition

Patient disposition and reasons for premature discontinuations and their frequencies will be tabulated.

Datasets analyzed

Number of patients in each analysis set will be tabulated and listings of any patients excluded from any analysis set will be provided.

Efficacy analysis

The primary efficacy endpoint has a composite numerator 'microbiologically confirmed TB and therapy initiated within 72 hours from admission' (success), 'non lab-confirmed TB or therapy

This project is part of the EDCTP2 programme supported by the European Union

not initiated within 72 hours' (failure).

Microbiological confirmation may arrive later than 72 hours after enrolment (to account for scenarios in which culture is requested or there is any delay on sample processing).

The primary efficacy analysis will be compared between the proportion of microbiologically confirmed TB and therapy initiated within 72 hours of enrolment in each study arm.

Adjustment for other variables (country, hospital, seasonality or other possible confounders) may be considered and will be described in detail in the analysis plan.

Missing values will be examined in detail. We may consider a multiple imputation procedure if necessary (variables with more than 10% of missing values).

We will accept as significant difference the p-values less than 0.05.

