10.5 Randomization

This is an individually randomized clinical trial. Eligible participants will be randomized to either the intervention or control arm, with an expected 50% of participants allocated to each of the arms. Randomization will be conducted using a web-based application (Enketo software) that can be used in any smartphone device or computer with internet connection. The day of randomization for each participant will be the enrolment day (study Day 0). At the time a participant is randomized, the study staff enters in the application several key data (patient study number and date of birth) and in reply, the randomization arm is provided a few seconds later in the same application interface. Thus, internet connection is needed for randomizing participants. Pre-registered users of the study team will be allowed to use the randomization application.

Developing a reliable training plan by which study teams (at the clinic and at the lab) are fully aware of the diagnostic allocation is critical so that arm-specific testing can be implemented without mistakes in a timely manner. This includes careful strategic measures (posters, signs, weekly meetings, etc) as part of the site internal planning, which also need to consider staff shifts, holidays (both in the hospital and at the laboratory). A screening and randomization log need to be daily updated. Day 0 CRF needs to be data entered in a timely manner to allow the central monitoring of number of recruited subjects per arm, site and week and overall mapping of participants included in the study.

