### 3.4 Endpoints

All study endpoints will be compared between control and intervention arm. Also, the final results will be presented disaggregated by sex.

3.4.1 The **primary endpoint** is the proportion of participants diagnosed with microbiologically confirmed TB and started on TB treatment within 72 hours of enrolment\* in whom TB is microbiologically confirmed\*/\*\*

\* The numerator of the primary endpoint includes participants per study arm who are diagnosed with microbiologically confirmed TB and initiated TB treatment within 72 hrs of enrolment. The denominator is the number of enrolled participants in each study arm.

\*\* Participants are defined to have microbiologically confirmed TB if at least one confirmatory TB test (Ultra, AlereLAM) gives a positive result.

**Secondary endpoints** are:

Related to main objective

3.4.2.1 Time-to-TB-treatment-initiation among microbiologically confirmed cases and among all TB cases since enrolment. We will estimate Kaplan Meier curves and hazard ratios at day 7, 14, 28 and 56. Additionally we will compare the time to related estimates (median and IQR) of intervention and control group.

3.4.2.2 Proportion of cases re-admitted to hospital. The numerator will be the number of admissions for any reason (not included in the exclusion criteria) after initial discharge and within 8 weeks from enrolment. The denominator will be the number of participants enrolled.

---

3.4.2.3 Proportion of participants who are diagnosed with TB (irrespective of bacteriological confirmation) and have started on TB treatment within 72 hours of enrolment.

3.4.2.4 Proportion of participants who are diagnosed with microbiologically confirmed TB and are started on treatment at 7, 14 days and 8 weeks of enrolment.

3.4.2.5 Time to laboratory confirmed TB diagnosis and any TB diagnosis since enrolment.

3.4.2.6 Proportion of microbiologically confirmed TB participants started on treatment without Rif resistance information (only AlereLAM positive)).

Related to secondary objectives.

3.4.2.7 Eight-week all-cause mortality. The numerator will be the number of deaths during eight weeks after enrolment, the denominator the number of participants enrolled.

3.4.2.8 In hospital and 4-week all-cause mortality among all participants enrolled (assessed as the eight-week all-cause mortality).

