## 5 Sample Size

We expect the absolute difference in proportions of bacteriological confirmation between the two arms to be 7% (from 19% to 26% from the control to the intervention arm). Sample size was chosen to be sufficient to detect a 36.8% relative increase in the primary outcome in the intervention arm (as compared to the control arm).

Under this premise and the following assumptions:

- Alpha (two sided): 0.05
- Beta (power 80%): 0.2
- Estimated proportions of participants with microbiologically confirmed TB in the control arm 19% and in the intervention arm 26%
- Lost to follow up: 5% of recruited participants.

The study will recruit 586 PLHIV participants per trial arm, then we will include in the analysis 1172 participants in total. This number of participants will come from 4 sites (293 participants per arm at each site).

For this calculation we have used the following formulas based on Normal asymptotic approximation for proportions:

Sample Size formula

$$n_1 = \frac{\left( Z_{1-\alpha/2} \sqrt{(1 + \varphi) \bar{p}_1 (1 - \bar{p}_1)} + Z_{1-\beta} \sqrt{\varphi p_1 (1 - p_1) + p_1 (1 - p_1)} \right)^2}{\varphi |p_1 - \bar{p}_1|^2}$$

Power formula

$$\varphi = \frac{1 - w_1}{w_1}$$

$$\bar{p} = \frac{p_1 + \varphi p_2}{1 + \varphi}$$

$$1 - \beta = \Phi \left( \frac{|p_1 - \bar{p}| \sqrt{\varphi w_1} - Z_{1-\alpha/2} \sqrt{(1 + \varphi) \bar{p} (1 - \bar{p})}}{\sqrt{\varphi p_1 (1 - p_1) + p_2 (1 - p_2)}} \right)$$

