## 10. Other Analyses

We will do a comparison of baseline characteristics between participants who can complete the study and participants who we will lose during their follow-up period. We will do this analysis to test if the participant loss is by chance. We will use Chi statistical test. The variables that we will test are: Country (COUNTRY), Sex (SEX), Ethnic group (ETHNIC), Level of education (EDUCATION), Employment Status (EMPLOYMENT), Early HIV positive result (EARLY\_HIV), Current taking antiretroviral (ART\_YN), Previous TB episodes (TB\_TX\_YN), Received BCG vaccination (BCG\_YN), Participant live alone? (ALONE), Patient taking cotrimoxazole (CTX\_YN), Karnofsky Performance Status Scale (KARNOFSKY), Patient's WHO clinical Stage (WHO\_STAGES) and TB treatment start (TB\_TX\_START\_YN).

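### Significance tests on baseline factors cannot show that loss is random, and the SAP has no clear rule for unknown vital status in 8-week mortality

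*Protocol*

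**What the plan says.** **Tests of loss.** Protocol 13.2.2 compares baseline characteristics of lost and non-lost patients, and across arms, in order to make sure that loss is random. It continues: "If we find any significant attribute we will adjust the analysis by this/these factors". SAP 10 gives the purpose as "We will do this analysis to test if the participant loss is by chance", names the chi-square test and lists 14 variables. SAP 10 itself repeats no adjustment rule. SAP 6.3 has a looser one, under which site, demographic and other baseline variables enter if differences are detected or if they look like confounders.

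**Mortality.** Protocol 8.2 makes eight-week all-cause mortality the main secondary endpoint. It defines it as deaths over enrolled and adds a second calculation with right-censoring at loss to follow-up. SAP 3.4.2.7 keeps only the first part: "The numerator will be the number of deaths during eight weeks after enrolment, the denominator the number of participants enrolled". SAP 8.2.1 analyses that proportion with a z test and a chi-square or Fisher test.

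**Missing data.** SAP 6.2 prescribes complete-case analysis when missingness is below about 5% and selective loss in one arm is implausible. Above 5% it prescribes a best/worst-case analysis for TB treatment initiation, time from enrolment and microbiological results. Vital status is not in that list. The sample size section of the SAP assumes: "Lost to follow up: 5% of recruited participants". Protocol 10.12 expects the same 5% at month 2.

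**The concern.** There are two separate problems.

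First, the tests are asked to do what they cannot. A significant result can arise by chance and would then change the model. A non-significant result, with few patients lost, says little. No comparison of baseline factors can exclude loss that depends on death itself.

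Second, the SAP does not say clearly what happens to a participant whose vital status at week 8 is unknown. Dividing deaths by everyone enrolled leaves that person in the denominator and out of the numerator, which has the same effect as recording survival. The complete-case rule would instead remove the person. The two give different estimates, and the expected loss lies at the point where the missing-data rule switches. At stake is how the main secondary endpoint is estimated, and whether a reader can see how far unknown vital status could move it.

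**Working it through.** **Inputs.** From the documents: 586 per arm and 1172 in total (SAP 5); 5% loss (SAP 5, Protocol 10.12); 14 tested variables (counted in SAP 10). Assumed: a 5% level for the loss tests, since none is stated for them and Protocol 13.2.2 uses 0.05 for most comparisons; and 8-week mortality of 10–30%, since the documents give no rate.

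**Plan's own figure.** For 19% v 26%, two-sided 0.05, 80% power and pooled variance:

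n = [1.96·√(2 × 0.225 × 0.775) + 0.8416·√(0.19 × 0.81 + 0.26 × 0.74)]² / 0.07² = 557.5, so 558 per arm.

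558 × 1.05 = 586; 558 / 0.95 = 588. The stated 586 reproduces. The 5% therefore gives 0.05 × 1172 = 58.6, about 59 lost, or about 29 per arm with 557 known.

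**False flags.** If loss is fully random and the tests are independent, P(at least one significant) = 1 − 0.95¹⁴ = 0.512. The expected number is 14 × 0.05 = 0.7. The variables are correlated, so 51% is an approximation.

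**Power of the tests.** Two-proportion power, 1113 followed v 59 lost:

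| Prevalence in followed | 10-point difference | 15-point difference |
|---|---|---|
| 20% | 46% | 76% |
| 30% | 38% | 67% |
| 50% | 32% | 62% |

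Within one arm (557 v 29), power for 10 points is 18–28%.

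**Bounds on mortality.** With 29 of 586 unknown, the lowest value (all alive) and the highest (all dead) differ by 29/586 = 4.9 points in each arm. For scale, the 95% half-width of the difference, 1.96·√(2m(1−m)/586), is 4.1, 4.6 and 5.0 points at m = 15%, 20% and 25%.

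**Extreme split.** Take equal mortality among those known, all lost alive in one arm and all lost dead in the other. At 20%, there are 111 deaths among the 557 known in each arm. The comparison is 111/586 = 18.9% v 140/586 = 23.9%, z = 2.06, p = 0.039. The same calculation gives p = 0.009 at 10% and p = 0.067 at 30%.

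**Milder cases.** If the lost die at twice the rate of those known (20% assumed), true mortality is (111 + 29 × 0.40)/586 = 20.9%. Counting the lost as alive gives 18.9%; complete case gives 111/557 = 19.9%. If this happens equally in both arms, it largely cancels in the difference. With 5% lost per arm and counted as alive, the bias in the difference is 0.05 times the between-arm gap in death rate among the lost. A 20-point gap gives 0.05 × 20 = 1 point.

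**The case against.** A reader might infer that the chi-square tests are the plan's only handling of loss, or that mortality has no protection. The documents do not support that. Protocol 8.2 promises the censored calculation, and Protocol 13.2.2 plans Kaplan-Meier and log-rank for time to mortality. Protocol 10.10 and 10.11 plan three calls, a home visit and documentation of household deaths. The SAP 4.4 variable tables assign death dates and the study-end date to Kaplan-Meier graphs. SAP 6.2 also compares intention-to-treat with per-protocol results, and the protocol allows multiple imputation above 10% missing.

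Much of this stands, but it does not close the gap. SAP 8.2.1 never names a censored mortality estimate. The per-protocol set in SAP 6.1.1 is defined by samples and results within 72 hours, so it says nothing about vital status at week 8. The imputation threshold is twice the expected loss. Censoring also assumes that loss is unrelated to death.

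It is also fair to say that the adjustment rule and the 14 tests sit in different documents. The 51% is thus the chance of a false flag in the SAP's tests. It becomes the chance of a changed model only if the protocol rule is applied to them. Adjusting for a baseline covariate in a randomised comparison is not in itself shown to cause bias here; the fault is that the choice is data-driven.

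Finally, deaths over enrolled is not an explicit rule that lost participants are alive. It has that effect if applied as written, while SAP 6.2 points the other way.

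**Conclusion.** The concern holds in two limited parts. The baseline tests cannot show that loss is random: there is about a 51% chance of a false flag (5% level, independence assumed), 32–46% power for a 10-point imbalance, and no ability to detect loss that depends on death. In addition, the SAP drops the protocol's censored mortality calculation, leaves a denominator that conflicts with its own complete-case rule, and omits vital status from the best/worst-case analysis, with expected loss on the 5% threshold.

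The 4.9-point gap is an extreme bound, not a forecast; a bias of about 1 point or less in the difference is more realistic under the milder cases shown. A reader might also infer that unrecorded deaths are the likely reason for loss. That is plausible, but the documents do not show it, and they plan active tracing and exclude people who intend to migrate. Loss by week 8 should matter little for the 72-hour primary endpoint. This is a worthwhile improvement to a secondary analysis, not a threat to the main result.

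**What to change.** - **SAP 10 and Protocol 13.2.2:** keep the lost-versus-followed comparison as a descriptive table, shown by arm, and delete the significance trigger.
- **Covariates:** name in advance any adjustment for the mortality comparison, for example site and baseline CD4. SAP 8.2.7 already uses both, with sex, for time to diagnosis.
- **SAP 8.2.1:** restore the protocol's censored analysis as a Kaplan-Meier difference at day 56 with a confidence interval, censoring at the last date known alive. State how participants with unknown vital status are treated in the simple proportion.
- **SAP 6.2:** add vital status to the best/worst-case variables and run this whatever the percentage missing. The crossed scenario there names the intervention arm for both the best and the worst outcome; correct it so that each arm takes one.

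The cost is SAP wording, a matching line in the protocol, and two extra rows in the mortality table. The analyses use death, visit and study-end dates that the SAP already lists, so no new data are needed.

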13.2.3 Pre-specified sub-analysis

- Primary and selected secondary endpoints among PLHIV with ≥ 200 CD4, < 200 CD4 and < 100 CD4 cells/mm³ and
- Primary and selected secondary endpoints among admitted HIV positive patients providing at least one sputum, stool and (or) one urine sample for testing.
- The primary and selected secondary endpoints will also be calculated among those who had their test result available and were started on treatment within 72h of enrolment in both arms (as in a classical per-protocol (PP) analysis).

Both the main clinical trial analyses (related to primary and secondary objectives) and that related to the exploratory objectives (oral swab Ultra and LumiraDx and urine FujiLAM sub-studies) will be expanded in separate statistical analysis plans.

